# **Total participants:**

The study plans to enroll approximately 72 subjects to two groups with 36 subjects in each group. This sample size is based on the estimated time difference of 10 seconds between intubation times with and without the box.

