## Statistical analysis plan:

#### Sample size calculation

Sample size calculation was done by using the two means equation in the Power and Sample Size Calculation program (Dupont and Plummer, 1990). Based on a study by Teoh et. al., (2019), the mean of intubation time for Glidescope was 31.2 seconds and Airway Scope was 20.6 seconds. A clinically significant effect of 10 seconds would be of interest. The two-tailed hypothesis testing concluded that each group needed 36 subjects to achieve a power of 80%, with an error rate of 5%. A total of 90 subjects will be enrolled in this study with an estimated dropout rate set at 20%, 45 subjects will be enrolled in each group.

Suggested citation for Power and Sample Size Software:

Dupont WD, Plummer WD: 'Power and Sample Size Calculations: A Review and Computer Program', Controlled Clinical Trials 1990; 11:116-28.

Reference article:

It is a standard practice to include a dropout rate of 20% for clinical trials so that the power of the study will not be affected by dropouts, missing data and other study deviations (https://online.stat.psu.edu/stat509/node/47/).

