# **Primary end point:**

Calculating time to intubate (TTI) which is defined as time duration from loss of twitch to confirmation of end tidal CO 2. Comparing time to intubate (TTI) between study and control group using a t-test to compare means.

Non-inferiority margin set at 15 seconds. Non- inferiority hypothesis (H  $_0$ : Mean TTI diff  $\geq$ 15 s, H  $_A$ : Mean TTI diff < 15 s).

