Statistical Analysis Plan

Date November 20, 2024

Title: Time to Adapt in the Pandemic Era: A Prospective Randomized Study Comparing Time to Intubate With and Without the Barrier Box

Principal Investigator: [name]

Sub-Investigators: [name], [name], [name]

Research Site: Guthrie Robert Packer Hospital, Department of Anesthesiology

National Clinical Trial Number: NCT04411056

Sample size calculation

Sample size calculation was done by using the two means equation in the Power and Sample Size Calculation program (Dupont and Plummer, 1990). Based on a study by Teoh et. al., (2019), the mean of intubation time for Glidescope was 31.2 seconds and Airway Scope was 20.6 seconds. A clinically significant effect of 10 seconds would be of interest. The two-tailed hypothesis testing concluded that each group needed 36 subjects to achieve a power of 80%, with an error rate of 5%. A total of 90 subjects will be enrolled in this study with an estimated dropout rate set at 20%, 45 subjects will be enrolled in each group.

Suggested citation for Power and Sample Size:

Dupont WD, Plummer WD: 'Power and Sample Size Calculations: A Review and Computer Program', Controlled Clinical Trials 1990; 11:116-28.

Reference article;

It is a standard practice to include a dropout rate of 20% for clinical trials so that the power of the study will not be affected by dropouts, missing data and other study deviations (https://online.stat.psu.edu/stat509/node/47/).

May 5, 2020 Statistical Consultant KV

The study plans to enroll approximately 72 subjects to two groups with 36 subjects in each group. This sample size is based on the estimated time difference of 10 seconds between intubation times with and without the box. (Protocol April 30, 2020)

Randomization:

Subjects will be randomized by block randomization. Randomization will be done by a random number generated computer program by someone not involved in the research. The randomization schedule will be placed in sealed envelopes to be concealed from the researcher until time of verbal consent.

Sealed Envelope Ltd. 2019. Simple randomisation service. [Online] Available from: https://www.sealedenvelope.com/simple-randomiser/v1/ [Accessed 6 May 2020].

Statistical Software

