R 3.5.3 software will be used for statistical analysis.

Non-Inferiority Study Design

Hypothesis

Use of the barrier box prolongs the mean TTI by more than 15 s compared to a control group with no barrier box

HO: Mean TTI changes with barrier box

HA: Mean TTI does not change with barrier box

Non-inferiority margin: Our research team decided to use 15 s as non-inferiority margin. The premise of our non-inferiority study is to compare the mean TTI and infer if the additional time taken for airway manipulation with a barrier box is within acceptable non-inferiority margin between the means of both the groups (Box vs No Box). Non-inferiority margin of 15 s is considered acceptable while comparing airway manipulation in both the groups based on our clinical experience and pilot study data. Our literature review showed that this non-inferiority margin ($\Delta = 15$ s) would be within safe period of apnea tolerated by most patients (Moon et.al.)

Baseline data

Descriptive statistics for baseline demographics will include:

- Age in years- mean (standard deviation)
- BMI mean (standard deviation)
- Sex (male or female) frequency, number of participants
- American Society of Anesthesiology (ASA) Physical Status frequency, number of participants. ASA Physical Status is a classification system to assess a patient's preanesthesia medical co-morbidities, and helps predict perioperative risk when used with other risk factors such as frailty, level of deconditioning and type of surgery.
 - \circ ASA 1 a normal healthy patient
 - \circ ASA 2 a patient with mild systemic disease
 - ASA 3 A patient with severe systemic disease
 - The study will exclude patients who are ASA 4 (a patient with severe systemic disease that is a constant threat to life) or ASA 5 (a moribund patient who is not expected to survive without the operation).

Continuous variables of age and body mass index (BMI) will be reported as mean and standard deviation. Categorical variables of Gender (Sex) and ASA Physical Status will be reported in frequency tables.

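### The stated 80% power with 36 per group belongs to a two-tailed test of a 10 s difference; no power, SD or assumed delay is given for the primary non-inferiority test against 15 s

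*SAP*

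**What the plan says.** **The calculation.** The sample size section appears in the SAP and, in the same words, in the protocol's statistical section. It takes its effect from a study of laryngoscopes in which "the mean of intubation time for Glidescope was 31.2 seconds and Airway Scope was 20.6 seconds". It adds that "A clinically significant effect of 10 seconds would be of interest" and concludes: "The two-tailed hypothesis testing concluded that each group needed 36 subjects to achieve a power of 80%, with an error rate of 5" per cent. Enrolment is then raised: "A total of 90 subjects will be enrolled in this study with an estimated dropout rate set at 20" per cent, which is 45 per group.

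**The 10 s elsewhere.** The protocol, under Total participants, describes it differently: "This sample size is based on the estimated time difference of 10 seconds between intubation times with and without the box". The SAP repeats that sentence and dates it to the protocol of April 30, 2020. The same protocol section gives the enrolment as follows: "The study plans to enroll approximately 72 subjects to two groups with 36 subjects in each group".

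**The primary analysis.** The protocol's statistical section, under Primary end point, says "Non-inferiority margin set at 15 seconds", with the null hypothesis that the mean difference is 15 s or more. The SAP, under Non-Inferiority Study Design, says "Our research team decided to use 15 s as non-inferiority margin" and cites clinical experience and pilot data without figures. Only the SAP's Primary endpoint section gives the sidedness and level: a one-sided two-sample t-test, significant at p < 0.05. That section also expects a longer time to intubate (TTI) with the box, without saying how much longer.

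**The concern.** The calculation and the primary analysis differ in sidedness, in the null value and in the distance to be detected. The calculation asks whether 36 per group can distinguish a 10 s difference from zero. The primary test asks whether the delay can be shown to be below 15 s. Power for the second question depends on 15 s minus the true delay, on the SD of TTI and on the one-sided level. The documents give no SD and no assumed delay.

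The 31.2 s and 20.6 s do not fill the gap. They contrast two devices, not box with no box, and they are means only.

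What is at stake is the justification of the sample size. The only power figure in the documents does not belong to the test that decides the trial. How far the true figure lies from 80% depends on which of its two meanings the 10 s carries. If 10 s is the expected delay, only 15 − 10 = 5 s of the margin remains.

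**Working it through.** **Inputs from the documents.** 36 per group, 80% power, two-tailed 5%, difference 10 s, or 31.2 − 20.6 = 10.6 s from the cited means (sample size section). Dropout 20% (same section). Margin 15 s (protocol, Primary end point; SAP, Non-Inferiority Study Design). One-sided t-test at p < 0.05 (SAP, Primary endpoint).

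**Not in the documents.** The SD of TTI and the true delay assumed for the non-inferiority test. Both are assumptions below.

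**Step 1: the plan's own figure.** By the normal approximation, n = 2·SD²·(1.960 + 0.842)²/d². With d = 10 s and SD = 15 s this is 2 × 225 × 7.85/100 = 35.3, which rounds up to 36. So 36 is consistent with an SD near 15 s, but cannot be derived without one. Solving the two-tailed noncentral-t power equation for SD at n = 36 and 80% power gives 14.9 s for d = 10 s and 15.8 s for d = 10.6 s. The dropout step reproduces: 36/(1 − 0.20) = 45 per group, 90 in total.

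**Step 2: power of the primary t-test.** The noncentrality is (15 − true delay)/(SD·√(2/n)), with 2n − 2 degrees of freedom. The one-sided 5% critical value is 1.667 for n = 36 and 1.662 for n = 45. With SD 14.9 s and n = 36, the standard error is 14.93 × √(2/36) = 3.52 s. The noncentrality is then 15/3.52 = 4.26 at no delay, 10/3.52 = 2.84 at 5 s, 7.5/3.52 = 2.13 at 7.5 s and 5/3.52 = 1.42 at 10 s. The same steps give the other rows.

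| Evaluable per arm | SD (back-solved) | 0 s | 5 s | 7.5 s | 10 s |
|---|---|---|---|---|---|
| 36 | 14.9 s | 99.5% | 88% | 68% | 41% |
| 36 | 15.8 s | 99.0% | 84% | 63% | 38% |
| 45 | 14.9 s | 99.9% | 93% | 76% | 47% |
| 45 | 15.8 s | 99.8% | 91% | 72% | 44% |

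At SD 14.9 s, power is 80% at a true delay of about 6.2 s with 36 per arm and about 7.1 s with 45.

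**Step 3: how far this depends on the assumptions** (36 per arm).

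- One-sided 5%, SD 10 s: over 99.9, 99.5, 93 and 68% at delays of 0, 5, 7.5 and 10 s.
- One-sided 5%, SD 20 s: 93, 68, 47 and 28% at the same delays.
- One-sided 5%, SDs outside that range: SD 8 s gives 84% at a 10 s delay, and SD 25 s gives 81% at no delay.
- One-sided 2.5%, which would apply if non-inferiority were read from a two-sided 95% interval for the difference, SD 14.9 s: 98.8, 80, 56 and 29%.

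**Step 4: which rule the figures describe.** All of them are for the t-test. The SAP's Primary endpoint section also says that the null is rejected if the difference in means is below 15 s. Taken literally as a rule on the observed difference, that would reject with probability of about Φ(5/3.52) = Φ(1.42) = 92% at a true delay of 10 s. It would also reject with probability Φ(0) = 50% at a true delay of exactly 15 s, so it is not a 5% test and cannot stand in for the t-test.

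**The case against.** The strongest reply is that 36 per group may be more than enough. If the box causes no true delay and the SD is near 15 s, the one-sided 5% test needs only about 13 per group for 80% power. That stands. A reader might infer from the 10 s column that the trial is underpowered. The documents do not support this: the column applies only if 10 s is the expected delay, and the SD is not known. But zero delay is not a stated assumption either. The SAP expects a longer TTI with the box, and the protocol's Total participants section calls 10 s the estimated difference.

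An SD must have been entered in the program, and it may come from the cited laryngoscope study or the pilot data. That also stands. The fair claim is that the SD is not stated, not that none was used.

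The protocol's short Statistics section names only a t-test of means, which a two-tailed calculation could fit. True, so the mismatch is sharpest within the SAP. The protocol's own statistical section nevertheless sets the 15 s null.

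A reader might also infer that a failed non-inferiority result could not be interpreted. That goes too far. The SAP plans means with 95% confidence intervals, and the observed difference with its interval would separate imprecision from a real delay. Planning inputs justify the sample size; they are not needed to read the result.

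On enrolment, the SAP dates the 72 to April 30, 2020 and the 90 to May 5, 2020, so the order is visible there. The protocol's Total participants section carries the 72 without any such mark.

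**Conclusion.** The concern holds as a mismatch between design and analysis. It is not an arithmetic error: 36 is consistent with an SD near 15 s, and 36/0.8 = 45 is correct. The only stated power, 80%, does not describe the primary test, and that test's power cannot be worked out from what the documents state.

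On the back-solved SDs and one-sided 5%, power with 36 evaluable per arm is about 99% at no delay, 84–88% at 5 s and 38–41% at 10 s. With 45 it is over 99%, 91–93% and 44–47%. These figures rest on an inferred SD, and other SDs change them widely. Inadequate power is not shown if the true delay is small.

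The two descriptions of the 10 s, and the two enrolment totals of 72 and 90 in the protocol, are separate inconsistencies that need reconciling.

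**What to change.** In the sample size section of both documents, say that the 80% and the 36 per group apply to the two-tailed 10 s comparison, and add the power of the primary test. For example:

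*The 36 per group were derived for a two-tailed 5% test of a 10 s difference (80% power, SD [value entered in the program; source]). The primary analysis is a one-sided 5% t-test against a 15 s margin. With this SD and an assumed true delay of [value] s, its power is [x]% with 36 and [y]% with 45 evaluable per group; for delays of 0, 5, 7.5 and 10 s it is [values]. These are planning assumptions, not trial results.*

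If the pilot data supplied the SD or a delay, cite them as the source. State whether 10 s is the expected delay or an effect of interest, and use that wording in the protocol's Total participants section and in both sample size sections. In Total participants, replace 72 (36 per group) with 90 enrolled (45 per group) to yield 36 evaluable per group. Mark the 72 quoted in the SAP as superseded.

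The cost is wording only. It needs no added patients and no change to the sample size, test, level or margin. The downside for the sponsor is a less favourable stated power at larger delays.

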For continuous variables, the two groups ("barrier box" or "no barrier box") will be compared using unpaired two-sample t-tests, if data meets assumptions for normally distributed data within each group and homogeneity of variances (equal variance between groups) For categorical variables, the two groups ("barrier box" or "no barrier box") at baseline will be compared using chi-square test of independence.

Primary endpoint

The primary end point is time to intubate (TTI) in seconds, from loss of twitch to confirmation of end tidal carbon dioxide.

TTI will be collected by an independent provider (registered nurse) not directly involved in airway management. The TTI is used as an outcome measure as it is an objective variable that can be measured and helps us in assessment of airway manipulation with a barrier box. We plan to use objective end points to eliminate inter- observer variability.

For the primary endpoint, mean TTI and 95% confidence intervals will be assessed and compared in the two groups, "barrier box" and control with "no barrier box".

An unpaired two-sample single-sided t-test will be used to test our non- inferiority hypothesis. The TTI of the barrier box group is expected to be higher than the mean TTI of control the group. Analysis will include two independent sample comparison of means using one sided t-test in R.

The t-test will be done based on assumptions that the sample has no dependence between subjects in the control group and the barrier box group. Similar variance in both the groups will be confirmed by Levine's test. With the sample size > 30, samples are expected to be from a population with a normal distribution. Results will be considered statistically significant when p < 0.05.

If the difference of the mean TTI between the groups is less than the non-inferiority margin of 15seconds, then the null hypothesis will be rejected.

Secondary endpoints and statistical analysis include:

- Attempts at intubation
 - o assessed as frequency (percentage) of patients intubated on first attempt.
- Need for bag mask ventilation (yes or no) during induction, defined as the time taken from propofol bolus to loss of twitches measured with a peripheral nerve stimulator.
 - assessed as frequency (number) of patients.
- Lowest oxygen saturation during induction (Lowest peripheral capillary oxygen saturation during induction, defined as the time taken from propofol bolus to loss of twitches measured with a peripheral nerve stimulator.

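### Meeting the 15 s margin supports only a mean delay below 15 s; the plan never relates that margin to the 10 s it calls clinically significant

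*SAP*

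**What the plan says.** **The 10 s figure.** The sample size section, in both the protocol and the SAP, states: "A clinically significant effect of 10 seconds would be of interest". It follows a comparison of two videolaryngoscopes (31.2 s and 20.6 s) and feeds a two-tailed calculation that gives 36 per group at 80% power and 5% error, raised to 45 for 20% dropout. The protocol's section on total participants ties the figure to this trial's own comparison: "This sample size is based on the estimated time difference of 10 seconds between intubation times with and without the box".

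**The 15 s figure.** The protocol's primary end point section says "Non-inferiority margin set at 15 seconds" and gives the alternative as a mean difference below 15 s. The SAP's section on the non-inferiority design says "Our research team decided to use 15 s as non-inferiority margin", and that this margin "is considered acceptable while comparing airway manipulation in both the groups based on our clinical experience and pilot study data". It adds that 15 s lies within the apnea period most patients tolerate, citing a published trial. The SAP's alternative hypothesis, unlike the protocol's, is that mean TTI is the same with the box.

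**The analysis.** The SAP's primary endpoint section plans a one-sided two-sample t-test at p < 0.05. If the difference in means "is less than the non-inferiority margin of 15seconds, then the null hypothesis will be rejected". On intervals it says "mean TTI and 95% confidence intervals will be assessed and compared in the two groups". On direction it says "The TTI of the barrier box group is expected to be higher than the mean TTI of control the group", without saying by how much.

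**The objective.** The protocol asks whether the box can be used with no significant delay in TTI. It does not define what counts as significant.

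**The concern.** Two values on the same endpoint carry clinical weight, and nothing connects them. One is a difference called clinically significant; the other is the largest delay that still counts as non-inferior. A result can rule out 15 s while leaving 10 s well inside the interval for the difference, and the plan has no wording for that result.

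Followed literally, the SAP's hypotheses and rejection rule turn a difference under 15 s into acceptance of an alternative that says mean TTI is unchanged. A delay of several seconds could then be reported as no change, or as a yes to the objective. The planned intervals are described for the two groups, and none is clearly named for the box minus no-box difference. The report might therefore not let a reader check whether 10 s has been excluded. What is at stake is the wording of the main conclusion, not the validity of the test.

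**Working it through.** **Inputs.** From the documents: 10 s, two-sided 5%, 80% power, 36 per group, 20% dropout, 45 per group, margin 15 s, one-sided test at 5%. Not in the documents: the SD of TTI. Everything below assumes equal SDs, the formal t-test, and either 36 per group or all 45 per group analysed.

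**1. The plan's own figures.** Without an SD, 36 per group cannot be reproduced from the stated inputs. Solving the two-sided t-test power equation (noncentral t, df = 2 × 36 − 2 = 70) for 80% power at 10 s gives SD = 14.93 s. The dropout step does reproduce: 36 / (1 − 0.20) = 45 per group, 90 in total. I use SD 14.93 s and show SD 20 and 10 s as the range.

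**2. Precision of the difference.** Standard error = SD × √(2/n). Half-width = t × standard error, with t at 0.95 for the one-sided limit and at 0.975 for the two-sided interval.

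| | 36 per arm | 45 per arm |
|---|---|---|
| Standard error | 14.93 × √(2/36) = 3.52 s | 14.93 × √(2/45) = 3.15 s |
| One-sided 95% half-width | 5.87 s | 5.23 s |
| Two-sided 95% half-width | 7.02 s | 6.26 s |

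**3. Results that meet 15 s but leave 10 s inside the 95% interval.** The test is met if the observed difference is below 15 − 5.87 = 9.13 s (36) or 15 − 5.23 = 9.77 s (45). The two-sided interval excludes 10 s only below 10 − 7.02 = 2.98 s (36) or 10 − 6.26 = 3.74 s (45). The window is as follows.

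| SD | 36 per arm | 45 per arm |
|---|---|---|
| 14.93 s | 2.98 to 9.13 s | 3.74 to 9.77 s |
| 20 s | 0.60 to 7.14 s | 1.62 to 7.99 s |
| 10 s | 5.30 to 11.07 s | 5.81 to 11.50 s |

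Using the one-sided limit that matches the test instead, the window at SD 14.93 s starts at 10 − 5.87 = 4.13 s (36) or 10 − 5.23 = 4.77 s (45).

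**4. Chance that a true 10 s delay meets the 15 s criterion.** Noncentral t with noncentrality (15 − 10) / standard error and one-sided 5%.

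| SD | 36 per arm | 45 per arm |
|---|---|---|
| 14.93 s | 0.406 | 0.472 |
| 20 s | 0.276 | 0.320 |
| 10 s | 0.676 | 0.761 |

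A true delay of 10 s lies inside a 15 s margin, so these are correct decisions about 15 s.

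**5. Test and two-sided interval against 15 s.** The two-sided interval excludes 15 s only below 15 − 7.02 = 7.98 s (36) or 15 − 6.26 = 8.74 s (45). Observed differences of 7.98 to 9.13 s (36) or 8.74 to 9.77 s (45) therefore meet the one-sided test while the two-sided interval includes 15 s. At an assumed true delay of 8 s this happens in about 13% and 12% of trials. Any reporting rule must say which limit decides.

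**The case against.** The best defence is that the SAP does say what delay is acceptable. It names 15 s, gives three grounds (clinical experience, pilot data, tolerated apnea), and poses the question as whether the added time falls within that margin. On this reading 15 s is the working meaning of a significant delay. The 10 s figure could simply be left over from a two-tailed difference calculation: it follows a comparison of two other devices, and the section that ties it to the box calls it an estimated difference, not a clinically significant one. Much of this stands. A reader might infer that 15 s is unjustified, or wider than the plan's own limit. The documents support neither, because a rationale is given and 10 s is nowhere stated to be the largest acceptable delay.

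It is also fair to say that a mandatory 10 s caveat would prejudge whether 10 s is a limit at all. That stands too, so the caveat should be conditional on the sponsor's answer.

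The defence does not remove the core point. The plan never says that 15 s defines a significant delay, the pilot figures are not shown, and no reading of either number makes a difference below 15 s equivalent to an unchanged mean.

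**Conclusion.** The point holds as one about interpretation. Meeting the margin supports a mean delay below 15 s. It does not exclude 10 s, does not support the SAP's alternative of an unchanged mean, and does not by itself answer the protocol's objective unless the plan states that 15 s is what significant means. If the upper limit also fell below 10 s, a stronger statement could be made.

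The size is illustrative because it rests on a back-solved SD. At 14.9 s, observed delays of roughly 3 to 9 s (36 per arm) or 4 to 10 s (45 per arm) would meet the test with 10 s still inside the 95% interval. The 41% and 47% pass rates at a true 10 s delay might be taken for an inflated type I error, but they are the expected behaviour of a 15 s margin. Whether 15 s is clinically right cannot be judged from the documents. The matter deserves correction because the change is cheap and governs the main conclusion.

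**What to change.** 1. **Conclusion.** Keep the 15 s margin and the one-sided 5% test. In the protocol's primary end point section and in the SAP's hypothesis and primary endpoint sections, state that if the test is met the conclusion is a mean delay of less than 15 s. Replace the SAP's alternative of no change with the protocol's alternative of a difference below 15 s.
2. **Interval.** In the SAP's primary endpoint section, report the box minus no-box difference in mean TTI with the upper one-sided 95% limit that matches the test and with the two-sided 95% interval, both shown against 10 s and 15 s. State that non-inferiority is judged by the one-sided limit, because the two-sided interval can include 15 s when the test is met.
3. **Reconciliation.** Beside the margin rationale in the SAP, the sponsor should say whether 10 s is a sizing figure or a clinically significant delay for this comparison, and give the pilot figures relied on. Only if 10 s is kept as clinically significant for box versus no box should the report state when 10 s is not excluded.
4. **Timing.** If outcome data have already been seen, label the wording as added afterwards and leave the margin unchanged.

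**Cost.** Wording only: no extra patients, and no change to the test or its power. The downside is a less favourable conclusion in some trials. If the 10 s qualification applies at the two-sided 95% limit, the chance of an unqualified conclusion at SD 14.9 s changes as follows.

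| True delay | 36 per arm | 45 per arm |
|---|---|---|
| 0 s | 0.995 to 0.80 | 0.999 to 0.88 |
| 5 s | 0.88 to 0.29 | 0.93 to 0.35 |

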 - assessed as mean and standard deviation
- Induction time defined as the time taken from propofol bolus to loss of twitches measured with a peripheral nerve stimulator.
 - o assessed as mean (in seconds) and 95% confidence intervals

For continuous variables, the two groups ("barrier box" or "no barrier box") will be compared using unpaired two-sample t-tests, if data meets assumptions for normally distributed data within each group and homogeneity of variances (equal variance between groups)

For categorical variable, the two groups ("barrier box" or "no barrier box") will be compared using chi-square test of independence.

Airway assessment data will be collected for the two groups ("barrier box" or "no barrier box") as frequency data (number of patients) and will include:

- Mallampati score (scale of 0 to 4) used to assess and prepare for possible difficult intubation of participants who score high. Lower scores are less likely to have a difficult intubation, and higher scores are more likely to have a difficult intubation.
- Number of patients will be assessed in both groups for each of these classes:
 - Mallampati 0 (Any part of the epiglottis is visible)
 - Mallampati 1 (soft palate, uvula, and pillars are visible)
 - Mallampati 2 (soft palate and uvula are visible)
 - Mallampati 3 (only the soft palate and base of the uvula are visible)
 - Mallampati 4 (only the hard palate is visible)
- Thyromental Distance (TMD) > 3 finger breadth
 - TMD is the distance from the thyroid notch to the chin when the head is extended. TMD is used to assess and prepare for possible difficult intubation of participants who are less than or equal to 3 finger breadth. A distance of greater than 3 finger breadth may be less likely to have a difficult airway or airway constriction

Number of patients with TMD > 3 finger breadth will be assessed in both groups

- Inter incisor distance > 3 finger breadth
 - Inter incisor distance is the distance between the upper and lower teeth of the open mouth of a patient. Inter incisor distance is used to assess and prepare for possible difficult intubation of participants who are less than or equal to 3 finger breadth. A distance greater than 3 finger breadth may be less likely to have a difficult airway or airway constriction

Number of patients with Inter incisor distance > 3 finger breadth will be assessed in both groups.

- Neck range of motion (Full or Restricted)

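### The primary TTI comparison is a valid but unadjusted t-test; adjusting for one or two baseline covariates named in advance could give a modest gain in precision at small risk

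*SAP*

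**What the plan says.** The SAP, under Primary endpoint, specifies: "An unpaired two-sample single-sided t-test will be used to test our non- inferiority hypothesis". It adds: "Analysis will include two independent sample comparison of means using one sided t-test in R". The protocol (Statistics, and Primary end point at its end) also names a t-test on means. Neither document plans a covariate-adjusted analysis of TTI, even as a sensitivity analysis.

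The covariates are available. The protocol's data sheet lists BMI and airway assessment in its pre-operative part. The SAP's Baseline data section says: "Continuous variables of age and body mass index (BMI) will be reported as mean and standard deviation". On the airway it says: "Airway assessment data will be collected for the two groups", as frequencies of Mallampati class, thyromental distance, inter-incisor distance and neck range of motion. The SAP describes each of these measures as indicating a more or less likely difficult intubation or airway. Their only planned use is tabulation and chi-square tests between arms; BMI is summarised and compared by t-test.

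Randomisation is blocked, and no stratification factor is named.

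**The concern.** The SAP treats the airway measures as prognostic but makes no use of that in its main comparison. In a trial with 36 evaluable patients per arm and no stratification, a baseline variable that predicts TTI can do two useful things in a prespecified model. It can reduce the residual variance, which narrows the interval set against 15 s. It can also account for a chance difference between arms in that variable.

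The planned between-arm tests do neither. After randomisation they ask whether a baseline difference arose by chance, which is already known, and the SAP does not say what would follow if one turned up. At stake is some precision on the primary endpoint, together with a rule, fixed before results are known, for handling an imbalance.

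**Working it through.** **Inputs from the documents.** Margin 15 s (SAP, Non-Inferiority Study Design). One-sided t-test, with the level given as: "Results will be considered statistically significant when p < 0.05". Planning effect: "A clinically significant effect of 10 seconds would be of interest". Sample size: 36 per group for 80% power, two-tailed, 5% error, and 45 per group after 20% dropout (SAP, Sample size calculation).

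**Inputs that must be assumed.** The SAP gives reference means ("the mean of intubation time for Glidescope was 31.2 seconds and Airway Scope was 20.6 seconds") but no SD. Neither document gives an R-squared between any covariate and TTI. I back-solve the SD and show R-squared from 0 to 30%. The true difference of 5 s is an illustration.

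**Step 1: the plan's own figure.** With n = 2·SD²·(1.960 + 0.842)²/10² and n = 36, SD = 10·√18/2.802 = 15.14 s by the normal approximation. The noncentral t gives 14.93 s. The 36 is therefore consistent with an SD near 15 s, but cannot be reproduced independently. The dropout step reproduces exactly: 36/(1 − 0.20) = 45 per group, 90 in all. I use 14.93 s below.

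**Step 2: unadjusted analysis.** SE = 14.93·√(2/36) = 3.52 s. At a true difference of 5 s the distance to the margin is 15 − 5 = 10 s, so the noncentrality is 10/3.52 = 2.84 on 70 df. Power is 80.0% at one-sided 2.5% and 87.9% at one-sided 5%. The 80.0% holds by construction, because the distance equals the 10 s planning effect.

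**Step 3: adjusted analysis.** With k covariate parameters and N = 72, the expected variance is multiplied by (1 − R²)·[1 + k/(N − k − 3)]. The second term is the cost of chance covariate imbalance. For k = 2 it is 1 + 2/67 = 1.030. Residual df are 72 − 2 − 2 = 68. Power comes from the noncentral t with noncentrality 10/SE.

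| R² | SE (s) | Change in SE | Power, one-sided 2.5% | Power, one-sided 5% |
|---|---|---|---|---|
| Unadjusted | 3.52 | – | 80.0% | 87.9% |
| 0 | 3.57 | +1.5% | 78.8% | 87.0% |
| 5% | 3.48 | −1.1% | 80.8% | 88.5% |
| 10% | 3.39 | −3.7% | 82.9% | 89.9% |
| 20% | 3.20 | −9.2% | 87.0% | 92.7% |
| 30% | 2.99 | −15.1% | 91.0% | 95.2% |

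**Step 4: break-even.** The variance falls only if R² exceeds k/(N − 3): 2/69 = 2.9% for two parameters, 1/69 = 1.4% for one, and 8/69 = 11.6% for eight. Eight is about what BMI plus indicators for every listed airway measure would need: BMI 1, five-class Mallampati 4, and 1 each for thyromental distance, inter-incisor distance and neck motion.

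**Step 5: other scenarios, at one-sided 5%.** With 45 evaluable per arm and a true difference of 5 s, power is 93.4% unadjusted and 94.0 to 94.9% for R² of 5 to 10%. With 36 per arm and no true difference, the unadjusted test already has 99.5%.

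**The case against.** The strongest reply is that nothing here is wrong. In a randomised trial with blocks and no named stratification factor, the unadjusted comparison is valid and unbiased, and its standard error already allows for chance imbalance. That stands in full.

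The size of the gain is also unknown. The SAP links the airway measures to difficult intubation, not to seconds of TTI, and treats BMI only as a demographic variable. The protocol excludes BMI above 35 and known or anticipated difficult airways, which truncates the range of these variables and probably lowers R-squared. At R-squared of 5 to 10% the gain at one-sided 5% is only about 0.6 to 2 points. This stands too, and it limits the point to a modest improvement.

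A reader might go further and infer that the plan throws precision away and that adjustment is free. The documents support neither. They give no R-squared, so a loss cannot be shown. Each covariate uses a degree of freedom and adds variance through imbalance, so power drops by about 1 point if the covariates explain nothing. Nor is a model with every airway measure better: below an R-squared of about 12% it would lose precision, and some cells would probably be sparse. Two covariates would also leave imbalance in the other airway measures unadjusted.

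There is a timing objection as well. The SAP is dated November 20, 2024, while its sample size text dates from May 2020 and the protocol planned 2 months of enrolment and 4 months to completion. The documents do not say whether outcomes had been seen by then. If they had, changing the primary analysis would be post hoc; the fix must allow for that.

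**Conclusion.** The point holds as a cheap, optional improvement. The primary t-test is sound; a model with one or two covariates fixed in advance may sharpen it. Under the stated assumptions (36 evaluable per arm, SD 14.93 s, true difference 5 s, two covariates), the SE falls by 1.1 to 15.1% as R-squared goes from 5 to 30%. The power gain is 0.8 to 11.0 points at one-sided 2.5%, or 0.6 to 7.3 points at the SAP's apparent one-sided 5%. The downside is about 1 point at R-squared 0. Given the exclusions, the low end is more likely. The gain depends on assumptions that the documents cannot confirm; the lack of any adjusted TTI analysis is plain in the text.

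**What to change.** In the SAP's Primary endpoint section, define the primary analysis as a linear model of TTI on arm, BMI (continuous) and Mallampati class (0–2 versus 3–4). Compare the upper confidence limit of the adjusted mean difference with 15 s, and state the confidence level. Without an interaction term the arm coefficient is still a mean difference in seconds, so the margin keeps its meaning. Keep the unadjusted t-test as a sensitivity analysis.

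Use BMI alone if Mallampati 3–4 is sparse. Set the count that triggers this in advance and apply it to both arms pooled, without reference to TTI.

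State in the SAP whether TTI data had been seen before November 2024. If they had, keep the t-test as primary, report the adjusted model as a sensitivity analysis and label it post hoc.

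The cost is a few lines of SAP and code, up to two degrees of freedom, and about 1 point of power if the covariates turn out not to be prognostic. No new data are needed.
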